14.3.4.2.3. Phase 3 Exploratory Endpoint Analysis

CCI

CCI

14.3.6. Safety Analysis

Safety analyses will be performed on the Safety Population, which includes all patients who receive at least one dose of study treatment. Patients will be analyzed according to the treatment actually received.

Phase 2 safety data will be integrated with the Phase 3 safety data in the final safety analysis.

The safety and tolerability of selinexor will be evaluated by means of drug-related AE reports, physical examinations, and laboratory safety evaluations. CTCAE, v.4.03 will be used for grading of AEs. Investigators will provide their assessment as either related or not related to study treatment.

TEAEs, SAEs, AEs of at least Grade 3 in severity, related AEs, and AEs leading to withdrawal of treatment will be summarized by treatment group and in the overall safety population. TEAEs will be those that start or worsen on or after the first day of study treatment, through 30 days after last dose; related AEs will be those with an Investigator determination of related to treatment. Laboratory data will be analyzed by summary statistics over time, as well as by shift tables based on CTCAE v. 4.03 grades of severity.

14.3.6.1. Adverse Events

AEs will be coded using the Medical Dictionary for Regulatory Activities (MedDRA) and displayed in tables and listings using MedDRA system organ class (SOC) and Preferred Term.

Analyses of AEs will be performed for those events that are considered treatment-emergent, where treatment-emergent is defined as any AE with onset or worsening of a pre-existing condition on or after the first dose of study treatment through 30 days following the last dose of study treatment, or any event considered drug-related by the Investigator through the end of the study. AEs with partial dates will be assessed using the available date information to determine if treatment-emergent; AEs with completely missing dates will be assumed to be treatment-emergent. No formal hypothesis-testing of AE incidence rates will be performed.

AEs will be summarized by patient incidence rates; therefore, in any tabulation, a patient contributes only once to the count for a given AE (preferred term). The number and percentage of patients with any TEAE will be summarized for each treatment group, classified by SOC and preferred term. The number and percentage of patients with TEAEs assessed by the Investigator as related to treatment will also be tabulated. The number and percentage of patients with any Grade ≥ 3 TEAE will be tabulated in the same manner.

The causal relationship between the occurrence of an AE and the study treatment will be judged by the Investigator as either related or not related to study treatment. In the event a patient experiences repeat episodes of the same AE, then the event with the highest severity and/or strongest causal relationship to treatment will be used for purposes of tabulations.

SAEs will also be tabulated.

All AEs (treatment-emergent and post-treatment) will be listed in by-patient data listings, classified by treatment, patient and day on study. In addition, separate by-patient listings will be provided for the following: patient deaths; serious AEs; and AEs leading to withdrawal.

14.3.6.2. Laboratory Data

Clinical laboratory values will be expressed using conventional SI units.

For each treatment arm, the actual value and change from baseline (Day 1, prior to the first administration of study treatment) to each on study evaluation will be summarized for each clinical laboratory parameter, including hematology, clinical chemistry, coagulation and urinalysis. In the event of repeat values, the last non-missing value per study day/time will be used. In the event that Day 1 data are unavailable for a given patient/parameter, the screening value will substitute as the baseline value.

Severity of select clinical lab measures will be determined using CTCAE criteria (eg, those measures that have a corresponding CTCAE grade classification). Labs with CTCAE grades greater than or equal to 3 will be presented in a data listing. Shift tables that present changes from baseline to worst on-study and baseline to last on-study values relative to CTCAE classification ranges will be produced.

14.3.6.3. Vital Signs and Physical Examinations

The actual value and change from baseline (Day 1, prior to the first administration of study treatment) to each on study evaluation will be summarized for vital signs.

By-patient listings of vital sign measurements will be presented in data listings.

Abnormal physical examination results at screening, and abnormal physical examination results (AEs) during the study, will be summarized. All physical examination findings will be presented in by-patient data listings.

14.3.6.4. Concomitant Medications

The use of concomitant medications will be included in by-patient data listings.

14.3.7. Procedures for Handling Missing Data

No imputation of missing efficacy data is planned for the primary analysis of efficacy endpoints. For patient reported QoL measurements, missing data will be handled as described in the *EORTC-QLQ-C30* and *EuroQoL EQ-5D-5L Scoring Manuals*. Additional sensitivity analyses will be done using the Jump to Reference (J2R) and last observation carried forward imputation approaches.

For time to event analyses, patients who have no efficacy evaluations will be considered as censored at time 0. For OS, patients will be censored on the date they were last known to be alive regardless of disease status.

For AEs, missing dates will not be imputed; however, if partial dates are available, they will be used to assess if the AE occurred during the treatment period. Missing severities of AEs will not be imputed and will be considered missing in any tabulations of AE severity. If an AE is missing a response to the question regarding relationship to treatment, the event will be considered to be related.

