7.5.1. Primary Efficacy Endpoint

- Progression-free survival (PFS), defined as the time from date of randomization until the first date of PD, per RECIST v. 1.1, or death due to any cause. Evaluation of the radiologic data for the primary PFS endpoint will be based on data from a scan review by the independent central reader.

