4.1. PRIMARY EFFICACY ENDPOINTS

4.1.1. Progression-Free Survival (PFS)

Progression-free survival (PFS), defined as the time from date of randomization until ICR-determined PD per RECIST v.1.1, or death due to any cause, whichever occurs first.

The primary analysis of PFS will be performed by treatment arm (selinexor versus placebo) using the Ph3-ITT population. The analysis will be repeated for the Ph3-PP population as a supportive analysis.

Duration is calculated as end date – start date +1. For instance, if a PFS event occurs, then PFS time (in days) is defined as event date – date of randomization +1. If a censoring event occurs, then PFS time is defined as the censoring date – date of randomization +1.

Please refer to Table 4-1 for details on PFS outcome status (PFS event vs. censored) and censoring definitions.

Table 4-1 PFS Outcome and Censoring Definitions

#	Situation	Date of event or censoring	Outcome
1	No baseline disease assessment	Randomization	Censored
2	No adequate post-baseline disease status assessment unless death occurs prior to first post-baseline assessment	Randomization	Censored
3	ICR-determined PD without a gap of 2 or more consecutively missed scheduled disease assessment before PD.	Date of PD	PFS Event
4	Death before ICR-determined PD and without a gap of 2 or more consecutively missed scheduled disease assessment before death.	Date of death	PFS Event
5	No ICR-determined PD or death on or before 
 • Database cut • Withdrawal of informed consent • Lost to follow-up • Date of discontinuation from blinded treatment + 30 days • A gap of 2 or more consecutively missed scheduled disease assessment • Start of new antineoplastic therapy*, whichever occurs first 	Date of last adequate disease assessment prior to the events listed in the left column	Censored

*For the purpose of calculating PFS for blinded treatment, start of open-label selinexor will be considered as initiating a new antineoplastic therapy.

The number and percentage of patients who had a PFS event will be reported. Median PFS with 95% confidence interval (CI) will be summarized using the Kaplan-Meier (KM) method for each treatment arm. The KM curves for PFS will be provided by treatment arm.

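### Protocol 14.3.7 and SAP Table 4-1 row 1 censor at the start with no exception for death, contrary to the PFS definition; few patients should be affected

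*Protocol*

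**What the plan says.** Protocol 7.5.1 gives PFS as "defined as the time from date of randomization until the first date of PD, per RECIST v. 1.1, or death due to any cause". SAP 4.1.1 agrees: the interval runs "until ICR-determined PD per RECIST v.1.1, or death due to any cause, whichever occurs first".

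Protocol 14.3.7 then sets a general rule: "For time to event analyses, patients who have no efficacy evaluations will be considered as censored at time 0". Only overall survival gets its own rule there (censoring when last known alive). Death is not mentioned for any other time-to-event endpoint.

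SAP Table 4-1 sets out PFS outcome and censoring row by row. Three rows matter most here:

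- Row 1: "No baseline disease assessment". Censored at randomization, with no exception.
- Row 2: "No adequate post-baseline disease status assessment unless death occurs prior to first post-baseline assessment". Censored at randomization, with death excepted.
- Row 4: "Death before ICR-determined PD and without a gap of 2 or more consecutively missed scheduled disease assessment before death". A PFS event at the date of death.

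The table does not say which row prevails when two apply. SAP 1.7, which lists changes to the protocol's statistical section, does not mention a departure from 14.3.7 in its legible text. Its redacted bullets stand under a list of endpoints that will not be analyzed.

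**The concern.** A death before the first scan is a PFS event by definition, and its date is known. Censoring that patient at time 0 does more than lose the event: it takes the patient out of every risk set, so the randomized patient contributes nothing to the comparison. Very early deaths are also the ones most likely to reflect toxicity or very rapid progression, so a rule that discards them is not neutral if the arms differ in how often they occur.

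As written, the protocol and the SAP can classify the same patient in opposite ways on the primary endpoint, and two rows of the SAP table can do so between themselves. SAP 4.2.2.1 reuses Table 4-1 for time to progression, so the row 1 gap carries over there for deaths due to progression.

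**Working it through.** The plan states no figure for this point, so the check is to classify patients under each rule.

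**Inputs.** Phase 3 scans fall at screening and about 6, 12, 18 and 24 weeks after first dose (Protocol 10.5.1.2). The first post-baseline scan is therefore due at about 6 × 7 = 42 days and the second at 12 × 7 = 84 days. Take a death on day 30. Since 30 < 42, no scheduled post-baseline scan has been missed, and the two-missed-assessments condition in row 4 cannot exclude the death.

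| Patient | PFS definition | Protocol 14.3.7 | SAP Table 4-1 |
|---|---|---|---|
| A. Baseline scan, dies day 30 | Event, day 30 | Censored at time 0 if a baseline scan is not an efficacy evaluation; otherwise not covered | Event, day 30 (rows 2 and 4) |
| B. No baseline assessment, dies day 30 | Event, day 30 | Censored at time 0 | Row 1: censored at randomization. Row 4: event, day 30 |
| C. Baseline scan, no later scan, no death | No event | Time 0 on the same condition as A | Censored at randomization (row 2) |

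**Patient A.** The protocol does not define an efficacy evaluation. If a baseline scan does not count, 14.3.7 contradicts the endpoint definition and SAP row 2. If it does count, the sentence reaches only patients with no assessment at all, that is, patient B. It then has the same gap as row 1 and still contradicts the endpoint definition. The exception is needed on either reading.

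**Patient B.** Row 4 does not require a baseline assessment, so rows 1 and 4 both apply and give opposite results. Row 2 shows that the authors saw the need for a death exception; row 1 does not carry it.

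**How many patients B.** Inclusion criterion 6 requires RECIST-measurable disease in Phase 3, Protocol 9.1.1 requires screening imaging, and Protocol 7.6 requires the sponsor to confirm key eligibility before randomization. A randomized patient with no baseline assessment should be rare, and one who also dies without centrally determined progression rarer still. The documents give no count of either.

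**Phase 2.** Protocol 14.3.4.1 calls for a formal PFS analysis of the 56 eligible Phase 2 patients. SAP 4.1.1 names only the Phase 3 ITT and per-protocol populations. The title of Table 4-1 carries no phase limit, and SAP 4.2.2.1 applies its rules to Phase 2 ITT patients for time to progression. The governing rule for Phase 2 PFS is thus left to inference.

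**A neighboring overlap.** Row 5 also censors at the last adequate assessment before "Date of discontinuation from blinded treatment + 30 days" if no event has occurred by then. A patient with a baseline scan who stops on day 5 and dies on day 38 (5 + 30 = 35 < 38 < 42) falls under row 5, while rows 2 and 4 point to an event. This is a separate question from the row 1 gap, but it has the same cause: no stated precedence.

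**The case against.** The strongest reply is that the SAP is the later and more specific document. The protocol provides for a SAP finalized before database lock. The SAP is based on protocol v9.0 and has a dedicated PFS table that counts patient A. The sentence in 14.3.7 stands under missing data, and a dated death is not missing. Row 1 should be almost empty.

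Most of this stands, and it rules out three stronger readings that a reader might infer:

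- *That early deaths are dropped from the Phase 3 primary analysis.* They are not, for patients with a baseline assessment: rows 2 and 4 count them.
- *That the hazard ratio is biased toward selinexor, or that the count toward 209 events is wrong.* That would require the literal protocol sentence to override the SAP table. A shift in the hazard ratio would also need an early-death rate and a difference between arms, and the documents give neither. A calculation on assumed rates would compare literal 14.3.7 with the SAP; it would not measure row 1, the remaining gap.
- *That 14.3.7 is the only written rule for Phase 2 PFS.* The use of Table 4-1 for Phase 2 time to progression makes this arguable at best.

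The reply does not remove the contradictions. The protocol sentence has not been amended, the legible text of SAP 1.7 does not record the departure, and row 1 conflicts with row 4 inside the SAP itself.

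**Conclusion.** The point holds as an error of specification with a small expected effect. Protocol 14.3.7 lacks the death exception that the endpoint definition requires and that SAP row 2 contains. SAP row 1 lacks it too and conflicts with row 4. Either rule, followed literally, would misclassify a death on the primary endpoint.

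For Phase 3 PFS the exposure left under the SAP is confined to patients randomized without a baseline assessment who then die. That it is small rests on the entry requirements being followed; no number can be attached to it from the documents. The point is not evidence of bias in the Phase 3 primary result.

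**What to change.** - **SAP Table 4-1, row 1:** add *unless death occurs, in which case row 4 applies*.
- **Protocol 14.3.7:** add the same exception, so that a patient with no efficacy evaluation who dies has a PFS event at the date of death. If the protocol is not amended, list the departure in SAP 1.7.
- **SAP 4.1.1:** state that Table 4-1 also governs the formal Phase 2 PFS analysis.

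While the table is open, a line on the order of precedence among its rows would also settle the overlap with row 5.

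The cost is a few words in the SAP. No new data are needed, since dates of death are collected in survival follow-up (Protocol 9.1.8 and 9.2.6). An entry in SAP 1.7 is cheaper than a protocol change, which needs the amendment and approvals in Protocol 16.9. Either should be done before database lock.

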14.4. Changes in the Conduct of the Study or Planned Analysis

All deviations from the original statistical analysis plan will be documented and provided in the final clinical study report.

14.5. Clinical Study Reports

A primary clinical study report (CSR) may be written based on all available patients' data following completion of the primary PFS analysis. The final CSR will be reported when all patients have completed the follow-up period, withdrawn consent, lost to follow-up, or have died.

15. DATA COLLECTION AND MANAGEMENT

15.1. Data Confidentiality

Information about study patients will be kept confidential and managed under the applicable laws and regulations. Those regulations require a signed patient authorization informing the patient of the following:

- What protected health information (PHI) will be collected from patients in this study
- Who will have access to that information and why
- Who will use or disclose that information
- The rights of a research patient to revoke their authorization for use of their PHI.

In the event that a patient revokes authorization to collect or use PHI, the Investigator, by regulation, retains the ability to use all information collected prior to the revocation of patient authorization. For patients that have revoked authorization to collect or use PHI, attempts should be made to obtain permission to collect follow-up safety information (eg has the patient experienced any new or worsened AEs) at the end of their scheduled study period.

The data collection system for this study uses built-in security features to encrypt all data for transmission in both directions, preventing unauthorized access to confidential participant information. Access to the system will be controlled by a sequence of individually assigned user identification codes and passwords, made available only to authorized personnel who have completed prerequisite training.

15.2. Site Monitoring

Before study initiation, at a site initiation visit or at an Investigator's meeting, Karyopharm personnel (or designated contract research organization) will review the protocol and CRFs with the Investigators and their staff. During the study, the monitor will visit the site regularly to check the completeness of patient records, accuracy of entries on the CRFs, adherence to the protocol and to Good Clinical Practice (GCP), progress of enrollment, and to ensure that study treatment is being stored, dispensed, and accounted for according to specifications. Key study personnel must be available to assist the monitor during these visits.

The Investigator must maintain source documents for each patient in the study, consisting of case and visit notes (hospital or clinic medical records) containing demographic and medical information, laboratory data, ECGs, and the results of any other tests or assessments. All information recorded on CRFs must be traceable to source documents in the patient's file. The Investigator must also keep the original signed ICF (a signed copy is given to the patient).

The Investigator must give the monitor access to all relevant source documents to confirm their consistency with the CRF entries. Karyopharm monitoring standards require full verification for the presence of informed consent, adherence to the inclusion/exclusion criteria and documentation of SAEs. Additional checks of the consistency of the source data with the CRFs are performed according to the study-specific monitoring plan.

15.3. Data Collection

This study will utilize Electronic Data Capture (EDC), the designated clinical site staff will enter the data required by the protocol into the eCRF. The eCRFs have been built using fully validated secure web-enabled software that conforms to 21 CFR Part 11 requirements. Clinical site staff will not be given access to the EDC system until they have been trained. Automatic validation programs check for data discrepancies in the eCRFs and allow modification or verification of the entered data by the Investigator staff.

The Investigator is responsible for assuring that the data entered into the eCRF is complete and accurate, and that entry and updates are performed in a timely manner.

Concomitant treatments and prior medications entered into the database will be coded using the WHO Drug Reference List, which employs the Anatomical Therapeutic Chemical classification system. Medical history/current medical conditions and AEs will be coded using the MedDRA terminology.

15.4. Database Management and Quality Control

Karyopharm personnel (or designated contract research organization) will review the eCRF data entered by investigational staff for completeness and accuracy. Electronic data queries stating the nature of the problem and requesting clarification will be created for discrepancies and missing values and sent to the investigational site via the EDC system. Designated Investigator site staff are required to respond promptly to queries and to make any necessary changes to the data.

At the conclusion of the study, after discrepancies and missing values have been completed and the data have been verified to be complete and accurate, the database will be declared locked.

For EDC studies, after database lock, the Investigator will receive a CD-ROM or paper copies of the patient data for archiving at the investigational site.

16. ETHICAL AND ADMINISTRATIVE OBLIGATIONS

16.1. Regulatory and Ethical Compliance

This clinical study was designed and shall be implemented and reported in accordance with the International Council for Harmonisation (ICH) Harmonized Tripartite Guidelines for Good Clinical Practice, with applicable local regulations (including European Directive 2001/20/EC and US Code of Federal Regulations (CFR) Title 21), and with the ethical principles that originate from the Declaration of Helsinki.

16.2. Responsibilities of the Investigator and Good Clinical Practice

16.3. Institutional Review Boards/Independent Ethics Committees

The protocol and the proposed ICF(s) must be reviewed and approved by a properly constituted IRB/IEC before study start. Prior to study start, the Investigator is required to sign a protocol signature page confirming his/her agreement to conduct the study in accordance with these documents and all of the instructions and procedures found in this protocol and to give access to all relevant data and records to Karyopharm monitors, auditors, designated agents of Karyopharm, IRBs/IECs and regulatory authorities as required.

16.4. Informed Consent

Eligible patients may only be included in the study after providing written (witnessed, where required by law or regulation), IRB/IEC-approved informed consent.

In addition to the signing of informed consent by their parents, adolescent patients (permitted only in countries in which adolescents have been approved by the national/local regulatory/ethical authority) should sign written Assent Forms (witnessed, where required by law or regulation).

Informed consent for blinded study treatment must be obtained before conducting any study-specific procedures (ie, all of the procedures described in the protocol). Informed consent for open-label selinexor must be obtained before any study-specific measures for open-label selinexor are conducted at the Open-label C1 D1 Visit. The process of obtaining informed consent should be documented in the patient source documents. The date when a patient's Informed Consent was actually obtained will be captured in their CRFs.

Karyopharm will provide to Investigators, in a separate document, proposed ICFs that are considered appropriate for this study and comply with the ICH GCP guideline and regulatory requirements. Any changes to the ICFs suggested by the Investigator must be agreed to by Karyopharm before submission to the IRB/IEC, and a copy of the approved version(s) must be provided to the Karyopharm after IRB/IEC approval.

Females of childbearing potential should be informed that taking the study treatment may involve unknown risks to the fetus if pregnancy were to occur during the study and agree that in order to participate in the study they must adhere to the contraception requirements for the duration of the study. If there is any question that the patient will not reliably comply, they should not be entered in the study.

